### 2.2. Secondary Objective(s)

For the overall sample and by subgroups as appropriate, the secondary objectives are to:

- Percentage of patients with severe asthma according **frequency of exacerbations** (1, 2,  $\geq 3$  exacerbations) at the 1 year of follow-up;
- Percentage of patients with severe asthma according frequency of exacerbations (1, 2,  $\geq 3$  exacerbations) at the 2 year of follow-up;
- Percentage of patients with severe asthma according frequency of exacerbations (1, 2,  $\geq 3$  exacerbations) at the 3 year of follow-up;
- Percentage of patients with severe asthma according frequency of exacerbations (1, 2,  $\geq 3$  exacerbations) at the 4 year of follow-up;

- Percentage of patients with severe asthma according **concomitant diseases** (number of observations, the mean value, the standard deviation) at the time of study enrollment;
- Percentage of patients with severe asthma according concomitant diseases (number of observations, the mean value, the standard deviation) at the 1 year of follow-up;
- Percentage of patients with severe asthma according concomitant diseases (number of observations, the mean value, the standard deviation) at the 2 year of follow-up;
- Percentage of patients with severe asthma according concomitant diseases (number of observations, the mean value, the standard deviation) at the 3 year of follow-up;
- Percentage of patients with severe asthma according concomitant diseases (number of observations, the mean value, the standard deviation) at the 4 year of follow-up;
- Percentage of patients with severe asthma according to parameters: **age** (the mean value, the standard deviation) at the time of study enrollment;
- Percentage of patients with severe asthma according to parameters: **sex** at the time of study enrollment;
- Percentage of patients with severe asthma with different phenotypes in terms of parameters: **IgE (IU/ml)** (the mean value, the standard deviation, the minimum value, median, maximum value) at the time of enrollment;
- Percentage of patients with severe asthma with different phenotypes in terms of parameters: IgE (IU/ml) (the mean value, the standard deviation, the minimum value, median, maximum value) at the 1 years of follow-up;
- Percentage of patients with severe asthma with different phenotypes in terms of parameters: IgE (IU/ml) (the mean value, the standard deviation, the minimum value, median, maximum value) at the 2 years of follow-up;
- Percentage of patients with severe asthma with different phenotypes in terms of parameters: IgE (IU/ml) (the mean value, the standard deviation, the minimum value, median, maximum value) at the 3 years of follow-up;
- Percentage of patients with severe asthma with different phenotypes in terms of parameters: IgE (IU/ml) (the mean value, the standard deviation, the minimum value, median, maximum value) at the 4 years of follow-up;
- Percentage of patients with severe asthma with different phenotypes in terms of **eosinophil levels in absolute values** in complete blood count (number of observations, the mean value, the standard deviation, the minimum value, median, maximum value) at the time of enrollment;
- Percentage of patients with severe asthma with different phenotypes in terms of eosinophil levels in absolute values in complete blood count (number of observations, the mean value, the standard deviation, the minimum value, median, maximum value) at the 1 year of follow-up;
- Percentage of patients with severe asthma with different phenotypes in terms of eosinophil levels in absolute values in complete blood count (number of observations, the mean value, the standard deviation, the minimum value, median, maximum value) at the 2 year of follow-up;

- Percentage of patients with severe asthma with different phenotypes in terms of eosinophil levels in absolute values in complete blood count (number of observations, the mean value, the standard deviation, the minimum value, median, maximum value) at the 3 year of follow-up;
- Percentage of patients with severe asthma with different phenotypes in terms of eosinophil levels in absolute values in complete blood count (number of observations, the mean value, the standard deviation, the minimum value, median, maximum value) at the 4 year of follow-up;
- Percentage of patients with severe asthma in the parameters: **of body mass index (kg/m^2)**, at the time of study enrollment;
- Percentage of patients with severe asthma in the parameters: **of smoking (smoker's index (pack-years))** at the time of study enrollment;
- Percentage of patients with severe asthma in the parameters: **of professional history** at the time of study enrollment;
- Percentage of patients with severe asthma in the parameters: **of family history** at the time of study enrollment;
- Parameters of **FEV1 (liters, percentage of predicted)** (the mean value, the standard deviation) **before** bronchodilator in patients with severe asthma at the time of study enrollment;
- Parameters of **FVC** (liters, percentage of predicted) (the mean value, the standard deviation) **before** bronchodilator in patients with severe asthma at the time of study enrollment;
- Parameters of **FEV1** (liters, percentage of predicted) (the mean value, the standard deviation) **post** bronchodilator in patients with severe asthma at the time of study enrollment;
- Parameters of **FVC** (liters, percentage of predicted) (the mean value, the standard deviation) **post** bronchodilator in patients with severe asthma at the time of study enrollment;
- Parameters of **FEV1** (liters, percentage of predicted) (the mean value, the standard deviation) **before** bronchodilator in patients with severe asthma at the 1 year of follow-up;
- Parameters of **FVC** (liters, percentage of predicted) (the mean value, the standard deviation) **before** bronchodilator in patients with severe asthma at the 1 year of follow-up;
- Parameters of **FEV1** (liters, percentage of predicted) (the mean value, the standard deviation) **post** bronchodilator in patients with severe asthma at the 1 year of follow-up;
- Parameters of **FVC** (liters, percentage of predicted) (the mean value, the standard deviation) **post** bronchodilator in patients with severe asthma at the 1 year of follow-up;
- Parameters of **FEV1** (liters, percentage of predicted) (the mean value, the standard deviation) **before** bronchodilator in patients with severe asthma at the 2 year of follow-up;
- Parameters of **FVC** (liters, percentage of predicted) (the mean value, the standard deviation) **before** bronchodilator in patients with severe asthma at the 2 year of follow-up;

- Parameters of FEV1 (liters, percentage of predicted) (the mean value, the standard deviation) post bronchodilator in patients with severe asthma at the 2 year of follow-up;
- Parameters of FVC (liters, percentage of predicted) (the mean value, the standard deviation) post bronchodilator in patients with severe asthma at the 2year of follow-up;
- Parameters of FEV1 (liters, percentage of predicted) (the mean value, the standard deviation) before bronchodilator in patients with severe asthma at the 3 year of follow-up;
- Parameters of FVC (liters, percentage of predicted) (the mean value, the standard deviation) before bronchodilator in patients with severe asthma at the 3year of follow-up;
- Parameters of FEV1 (liters, percentage of predicted) (the mean value, the standard deviation) post bronchodilator in patients with severe asthma at the 3 year of follow-up;
- Parameters of FVC (liters, percentage of predicted) (the mean value, the standard deviation) post bronchodilator in patients with severe asthma at the 3year of follow-up;
- Parameters of FEV1 (liters, percentage of predicted) (the mean value, the standard deviation) before bronchodilator in patients with severe asthma at the 4 year of follow-up;
- Parameters of FVC (liters, percentage of predicted) (the mean value, the standard deviation) before bronchodilator in patients with severe asthma at the 4 year of follow-up;
- Parameters of FEV1 (liters, percentage of predicted) (the mean value, the standard deviation) post bronchodilator in patients with severe asthma at the 4 year of follow-up;
- Parameters of FVC (liters, percentage of predicted) (the mean value, the standard deviation) post bronchodilator in patients with severe asthma at the 4 year of follow-up;
- ;
- Percentage of patients with uncontrolled severe asthma based on the analysis of the questionnaire ACQ-6 at the time of study enrollment;
- Percentage of patients with uncontrolled severe asthma based on the analysis of the questionnaire ACQ-6 at the 1 year of follow-up;
- Percentage of patients with uncontrolled severe asthma based on the analysis of the questionnaire ACQ-6 at the 2 year of follow-up;
- Percentage of patients with uncontrolled severe asthma based on the analysis of the questionnaire ACQ-6 at the 3 year of follow-up;
- Percentage of patients with uncontrolled severe asthma based on the analysis of the questionnaire ACQ-6 at the 4 year of follow-up;
- **Mean number of exacerbations** (the mean value, the standard deviation) **requiring medical attention** (outpatient prescription of systemic corticosteroids) in patients with severe asthma at the time of study enrollment;
- Mean number of exacerbations (the mean value, the standard deviation) requiring medical attention (outpatient prescription of systemic corticosteroids) in patients with severe asthma at the 1year of follow-up;
- Mean number of exacerbations (the mean value, the standard deviation) requiring medical attention (outpatient prescription of systemic corticosteroids) in patients with severe asthma at the 2 year of follow-up;

- Mean number of exacerbations (the mean value, the standard deviation) requiring medical attention (outpatient prescription of systemic corticosteroids) in patients with severe asthma at the 3 year of follow-up;
- Mean number of exacerbations (the mean value, the standard deviation) requiring medical attention (outpatient prescription of systemic corticosteroids) in patients with severe asthma at the 4 year of follow-up;
- **Mean number of hospitalizations** (the mean value, the standard deviation) in patients with severe asthma at the time of inclusion in the study;
- Mean number of hospitalizations (the mean value, the standard deviation) in patients with severe asthma at the time of inclusion in the 1 year of follow-up;
- Mean number of hospitalizations (the mean value, the standard deviation) in patients with severe asthma at the time of inclusion in the 2 year of follow-up;
- Mean number of hospitalizations (the mean value, the standard deviation) in patients with severe asthma at the time of inclusion in the 3 year of follow-up;
- Mean number of hospitalizations (the mean value, the standard deviation) in patients with severe asthma at the time of inclusion in the 4 year of follow-up;
- **Percentage of patients with severe asthma** (the mean value, the standard deviation) taking high doses of **ICS/LABA, ICS/LABA+LAMA as maintenance therapy, biologics** at the time of study enrollment;
- Percentage of patients with severe asthma (the mean value, the standard deviation) taking high doses of ICS/LABA, ICS/LABA+LAMA as maintenance therapy, biologics at the 1 year of follow-up;
- Percentage of patients with severe asthma (the mean value, the standard deviation) taking high doses of ICS/LABA, ICS/LABA+LAMA as maintenance therapy, biologics at the 2 year of follow-up;
- Percentage of patients with severe asthma (the mean value, the standard deviation) taking high doses of ICS/LABA, ICS/LABA+LAMA as maintenance therapy, biologics at the 3 year of follow-up;
- Percentage of patients with severe asthma (the mean value, the standard deviation) taking high doses of ICS/LABA, ICS/LABA+LAMA as maintenance therapy, biologics at the 4 year of follow-up;
- **Percentage of patients with severe asthma** (the mean value, the standard deviation) **taking OCS as a maintenance therapy** at the time of study enrollment;
- Percentage of patients with severe asthma (the mean value, the standard deviation) taking OCS as a maintenance therapy at the 1 year of follow-up;
- Percentage of patients with severe asthma (the mean value, the standard deviation) taking OCS as a maintenance therapy at the 2 year of follow-up;
- Percentage of patients with severe asthma (the mean value, the standard deviation) taking OCS as a maintenance therapy at the 3 year of follow-up;
- Percentage of patients with severe asthma (the mean value, the standard deviation) taking OCS as a maintenance therapy at the 4 year of follow-up;

- **Percentage of patients with severe asthma** (the mean value, the standard deviation) **who have been changed therapy** (step up, step down by GINA) to 1 year of follow-up;
- Percentage of patients with severe asthma (the mean value, the standard deviation) who have been changed therapy (step up, step down by GINA) to 3 year of follow-up;
- Percentage of patients with severe asthma (the mean value, the standard deviation) who have been changed therapy (step up, step down by GINA) to 4 year of follow-up;
- **Percentage of patients with severe asthma who called for emergency medical care** for asthma (number of observations, the mean value, the standard deviation, median) at the 1 year of follow-up;
- Percentage of patients with severe asthma who called for emergency medical care for asthma (number of observations, the mean value, the standard deviation, median) at the 2 year of follow-up;
- Percentage of patients with severe asthma who called for emergency medical care for asthma (number of observations, the mean value, the standard deviation, median) at the 3 year of follow-up;
- Percentage of patients with severe asthma who called for emergency medical care for asthma (number of observations, the mean value, the standard deviation, median) at the 4 year of follow-up;
- **Percentage of patients with severe asthma who had disability sheets for asthma** (number of observations, the mean value, the standard deviation, median) at the 1year of follow-up;
- Percentage of patients with severe asthma who had disability sheets for asthma (number of observations, the mean value, the standard deviation, median) at the 2 year of follow-up;
- Percentage of patients with severe asthma who had disability sheets for asthma (number of observations, the mean value, the standard deviation, median) at the 3year of follow-up;
- Percentage of patients with severe asthma who had disability sheets for asthma (number of observations, the mean value, the standard deviation, median) at the 4 year of follow-up;

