### 3.0. METHODOLOGY

### 3.1. Registry Design

The Russian Severe Asthma Registry is a prospective multicenter, non-interventional observational study for patients with severe bronchial asthma (SA).

All patients included in the RSAR platform will be periodically observed during routine visits to the hospital with a follow-up of up to five years.

In the RSAR conductance there is no provision for any intervention in routine clinical practice, including the use of the study therapy / treatment methods or special research methods. From the day the project begins, the physician will collect data on all patients with SA who have visit as outpatient or hospitalized patient and who meet the inclusion criteria for in this study.

The study includes a retrospective part - an analysis of the medical records of patients available at the time of their inclusion in the study.

Patients with a confirmed diagnosis of SA (according to inclusion criteria) will be included in the study sequentially and observed for 5 years.

The period of patient's inclusion - from 03.2018 till 11.2022.

The observation period is from 03.2018 till 11.2022.

The approximate period of the Registry work is from 03.2018 to 12.2022.

The target sample size is up to 7,000 patients with SA over a period of 5 years.

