### 3.2. Draft Cities Initiation

The participation of cities and recruitment of patients in the RSAR is expected:

Period, years	Number of participating cities (health facilities)	Number of SA patients CRFs
03.2018-12.2018	30 (100 health facilities)	2000
01.2019-12.2019	30 (100 health facilities))	2000
01.2020-12.2020	30 (100 health facilities))	1000
01.2021-12.2021	30 (100 health facilities)	1000

01.2022-11.2022	30 (100 health facilities))	1000
-----------------	-----------------------------	------

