#### **4.4. Statistics analysis**

Primary and secondary statistical indicators will be presented using descriptive statistics methods. Qualitative variables will be presented in the form of incidence and percentage. The quantitative variables will be represented by numerical values, standard deviation indicators, minima and maxima, median and interquartile range. The frequency and severity of adverse events / reactions will be documented according to the Medical Dictionary of Regulatory Terminology, version 16.1. When analyzing the outcome of the disease among patients on therapy (drug), statistical analysis will be performed in a subgroup of newly identified patients. Evaluation of the outcome of SA can be determined by achieving a sufficient number of patients in a subgroup of newly identified patients and patients undergoing therapy (SA). The lack of comparison between groups of patients is due to the inaccuracy of these therapies in the history and treatment approaches.

In the course of the analysis, the standard statistical characteristics of morbidity, prevalence of the disease (SA) and their dependence on the basic demographic indicators (sex, age) will be assessed. The statistical analysis of the endpoints will be performed for patients with a diagnosis period of no more than 6 months from the date of inclusion in the register (a subgroup of newly identified patients) and also when the required amount of statistical data is collected within the register database.

The analysis will use standard methods of descriptive, frequency, logistic statistical analysis.

Hypotheses of the study. The main goal of the study is to obtain statistical estimates of the target epidemiological characteristics, formally asking questions about hypotheses of the study in this case is not applicable. After receiving the estimates, they are expected to be compared with similar ones, known in the foreign and domestic literature and official statistics.

Within the Registry, measures should be taken to collect data on the maximum number of patients within the claimed sample. In the absence of information within the fields of the individual registration card, the validating authority should separate information on the statuses "negative value", "no data", "not investigated".

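### Outcomes reported at both enrolment and years 1-4 are planned as separate summaries on shrinking, earlier-enrolled subsets, so a change in who is followed can look like a change in disease.

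*Combined protocol and SAP*

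**What the plan says.** Section 2.2 gives the ACQ-6 outcome first as "Percentage of patients with uncontrolled severe asthma based on the analysis of the questionnaire ACQ-6 at the time of study enrollment" and then as a separate item for each year, ending with "Percentage of patients with uncontrolled severe asthma based on the analysis of the questionnaire ACQ-6 at the 4 year of follow-up". The same layout is used for exacerbation category, mean exacerbations, concomitant diseases, IgE, blood eosinophils, FEV1 and FVC, hospitalisations, maintenance therapy and maintenance OCS.

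On method, section 4.4 states: "Primary and secondary statistical indicators will be presented using descriptive statistics methods". It also names logistic analysis, but with no outcome, covariates or purpose. Section 4.5 specifies summary statistics and percentages. Neither section specifies change from enrolment, a fixed cohort, a transition table or a longitudinal model.

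The calendar is in section 3.1: "The period of patient's inclusion - from 03.2018 till 11.2022" and "The observation period is from 03.2018 till 11.2022". The same section says that patients "will be included in the study sequentially and observed for 5 years". The target is stated as "The target sample size is up to 7,000 patients with SA over a period of 5 years", and section 3.2 splits it by period under the column "Number of SA patients CRFs".

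**The concern.** Recruitment runs to the day observation ends, so each later yearly summary loses the most recent entrants by design, even with no dropout. The enrolment figure describes everyone, while the year-4 figure can describe only patients who entered in 2018. If early entrants differ from later ones, or if patients who stay differ from those who leave, the series from enrolment to year 4 moves although no patient has changed.

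Section 2.0 sets out to monitor management and to evaluate the efficacy and safety of prescribed drug treatment. That aim invites readers to compare enrolment with the follow-up years. As the tables are planned, they could not tell disease change from a change in composition. Using the correct denominator at each year would not settle this, because the enrolment figure beside it would still rest on all entrants.

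**Working it through.** **Inputs from the plan.** Section 3.2 gives 2,000 patients in 03-12.2018 (10 months), 2,000 in 2019, 1,000 in 2020, 1,000 in 2021 (12 months each), and 1,000 in 01-11.2022 (11 months). Section 3.1 closes both inclusion and observation in 11.2022.

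**Plan's own total.** 2,000 + 2,000 + 1,000 + 1,000 + 1,000 = 7,000, which agrees with section 3.1. The months sum to 10 + 12 + 12 + 12 + 11 = 57.

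**Patients who can reach year k.** These are the patients enrolled by month 57 - 12k. I assume one CRF per patient, uniform recruitment within each period and no dropout.

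| Year | Enrolled by month | Count | Share of 7,000 |
|---|---|---|---|
| 1 | 45 | 2,000 + 2,000 + 1,000 + 1,000×11/12 = 5,917 | 84.5% |
| 2 | 33 | 2,000 + 2,000 + 1,000×11/12 = 4,917 | 70.2% |
| 3 | 21 | 2,000 + 2,000×11/12 = 3,833 | 54.8% |
| 4 | 9 | 2,000×9/10 = 1,800 | 25.7% |
| 5 | none | 0 | 0% |

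The documents give no dropout rate. At an assumed 5%, 10% or 20% per year, the year-4 count falls to 1,800×0.95⁴ = 1,466, 1,800×0.90⁴ = 1,181 or 1,800×0.80⁴ = 737.

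**Apparent shift with no patient changing.** Let a be the rate in 2018 entrants and b the rate in later entrants. Enrolment shows (2,000a + 5,000b)/7,000. Year 4 shows a, because everyone in it entered in 2018. The difference is (5,000/7,000)(a - b) = 0.714(a - b). The rates below are assumptions.

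| a | b | Enrolment | Year 4 | Apparent shift |
|---|---|---|---|---|
| equal | equal | same | same | 0 |
| 50% | 45% | 46.4% | 50.0% | +3.6 points |
| 60% | 40% | 45.7% | 60.0% | +14.3 points |

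In the last row the intermediate years would read 46.8%, 48.1% and 50.4%, a steady false worsening. If a is below b, the shift has the opposite sign.

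**Dropout alone.** Suppose there is no cohort difference, 50% are uncontrolled, and yearly retention is 85% in uncontrolled and 95% in controlled patients (assumed). Year 4 then shows 0.85⁴/(0.85⁴ + 0.95⁴) = 0.522/(0.522 + 0.815) = 39.1%, a false improvement of 10.9 points. With retention of 90% and 95% it shows 44.6%.

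**Scale.** At 50%, the 95% half-width is 1.96×√(0.25/1,800) = 2.3 points at year 4 and 1.96×√(0.25/7,000) = 1.2 points at enrolment. Shifts of this kind can exceed sampling error.

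**Effect of same-patient figures.** In each example the enrolment figure for the patients seen at year 4 equals their year-4 figure, so the change prints as zero.

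**The case against.** The plan is descriptive. Section 4.4 disclaims formal hypotheses and says that the estimates will be set against the literature and official statistics. No contrast of enrolment with year 4 is planned, and the primary objective in section 2.1 concerns enrolment only. That is correct, and it limits the weight of the point. It does not remove it, because section 2.0 invites the comparison and most of section 2.2 supplies the figures for it.

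Safeguards exist. Sections 4.4 and 4.8 plan to compare the characteristics of patients who leave with those who complete observation, and section 4.5 reports numbers of observations and a missing category. These would show attrition, but they correct no yearly figure. Nor do they clearly cover patients cut off by the 11.2022 close, who have not dropped out.

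Four stronger readings are tempting, and the documents do not support them.

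- A reader might infer that the enrolment and year-4 figures come from different people. They do not: the year-4 patients are a nested subset of those in the enrolment table.
- A reader might infer that no within-patient change is planned anywhere. The GINA step-up/step-down item in section 2.2 is one, though it covers only therapy steps and lists years 1, 3 and 4.
- A reader might infer that every objective is affected. Age, sex, BMI, smoking, professional and family history are enrolment-only; emergency calls and disability sheets are listed for years 1-4 only.
- A reader might infer that the planned tables forgo a large gain in precision. With common variance s², n patients at year 4 inside N at enrolment and within-patient correlation ρ, the planned contrast has variance s²(1/n + 1/N - 2ρ/N) and the paired change 2s²(1 - ρ)/n. At ρ = 0.5 both equal s²/n. Pairing is more precise only above 0.5 and less precise below it. The case for it is comparability.

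**Conclusion.** The point holds for outcomes summarised at both enrolment and years 1-4. The patient mix must change, from 7,000 at enrolment to at most about 1,800 at year 4, all of them 2018 entrants, and the planned tables cannot separate that from disease change. The counts rest on uniform recruitment within periods, full accrual of 7,000 and no dropout. They also precede any restriction to the newly identified subgroup mentioned in section 4.4.

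The size of the distortion is not known. It is zero if early and later entrants have equal rates and retention does not depend on the outcome. It is about 3.6 points at 50% versus 45% and about 14 points at 60% versus 40%. Nothing in the documents indicates that 2018 entrants differ from later ones, so these figures show what could happen and do not predict it. The change is worth making because it is cheap and affects most of the follow-up results; the primary objective is untouched.

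**What to change.** Add to section 4.5, for each outcome summarised at both enrolment and years 1-4:

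- beside each yearly figure, the number eligible by calendar, the number observed, and the enrolment figure for the same patients;
- the within-patient change from enrolment with its 95% interval;
- for categorical outcomes (exacerbation category, ACQ-6 control status, therapy group), a transition table of enrolment by year. For exacerbations this needs a zero category, which section 2.2 does not list.

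State which visit supplies each yearly value, since section 3.7 leaves visits to routine care; the planned yearly figures need that rule in any case.

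The cost is programming, with no new data collection, and two cautions to print with the tables. First, section 3.5 admits some patients because of poor control or frequent exacerbations, so part of any paired improvement may be regression to the mean. The interval does not allow for that. Second, same-patient figures remove composition from the contrast but do not make those still followed representative of all entrants. The dropout comparison in sections 4.4 and 4.8 should therefore stay.

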91	Drugs to manage asthma	Is the patient currently taking ICS (only)? (please select from the list)	No triamcinolone acetonide mometasone furoate fluticasone propionate fluticasone furoate ciclesonide flunysonide budesonide beclomethasone other
92	Drugs to manage asthma	- Date of start / end of ICS intake	DD / MM / YYYY
93	Drugs to manage asthma	Is the patient currently taking LABA (only)? (please select from the list)	No formoterol salmeterol indacaterol olodaterol other
94	Drugs to manage asthma	- Date of start / end of LABA intake	DD / MM / YYYY
95	Drugs to manage asthma	Is the patient currently taking LAMA (only)? (please select from the list)	No aclidinium tiotropium umeclidinium glycopyrronium

			other
96	Drugs to manage asthma	- Date of start / end of LAMA intake	DD / MM / YYYY
97	Inhalation technique assessment.	Appropriate Inappropriate (if so, the next question) Crucial mistakes Present Absent	
98	Drugs to manage asthma	Is the patient currently taking theophylline? (please select from the list)	No theophylline aminophylline other
99	Drugs to manage asthma	- Date of start / end of theophylline intake	DD / MM / YYYY
100	Drugs to manage asthma	Is the patient currently receiving a leukotriene receptor antagonist (LTRA)? (please select from the list)	No zafirlukast montelukast other
101	Drugs to manage asthma	- Date of start / end of LTRA intake	DD / MM / YYYY
102	Drugs to manage	Is the patient currently receiving treatment targeted on	No/Yes

	asthma	immunoglobulin E (Anti-IgE)? (omalizumab is prescribed)	
103	Drugs to manage asthma	Date of start / end of Anti-IgE intake?	DD / MM / YYYY
104	Drugs to manage asthma	Is the patient currently receiving treatment targeted on IL-5 (Anti-IL-5)? (please select from the list)	No reslisumab mepolizumab benalizumab dupilumab (?) tezepelumab (?) other (new biotechnological preparations will be added after approval and start of use in Russia)
105	Drugs to manage asthma	Date of start / end of Anti-IL5 intake?	DD / MM / YYYY
106	Drugs to manage asthma	Does the patient currently receive antibiotic treatment with the macrolide group? (please select from the list)	No azithromycin clarithromycin erythromycin roxithromycin fidaxomycin telithromycin other
107	Drugs to manage	Date of start / end of macrolide	DD / MM / YYYY

	asthma	intake?	
108	Compliance	Is there a non-compliance with the treatment regimen?	No Yes: - dosage; - frequency of reception; - absence of all prescribed medications; - other

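### Biologic use is tabulated by follow-up year pooled over 57 months of entry, so the change across the columns mixes entry cohorts and may match no cohort's change

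*Combined protocol and SAP*

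**What the plan says.** Section 2.2 defines one percentage for high-dose ICS/LABA, ICS/LABA+LAMA and biologics at enrolment and at each of years 1 to 4, the last worded "taking high doses of ICS/LABA, ICS/LABA+LAMA as maintenance therapy, biologics at the 4 year of follow-up". Maintenance OCS has the same time axis, ending with "taking OCS as a maintenance therapy at the 4 year of follow-up". The list is introduced by "For the overall sample and by subgroups as appropriate", with no subgroup named.

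Section 3.1 sets the dates: "The period of patient's inclusion - from 03.2018 till 11.2022" and "The observation period is from 03.2018 till 11.2022". It also gives the size: "The target sample size is up to 7,000 patients with SA over a period of 5 years". Section 3.2 spreads this over calendar periods under the column "Number of SA patients CRFs": 2000, 2000, 1000, 1000 and 1000 for 2018 to 2022.

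Item 104 of the appendix, the anti-IL-5 field, notes that "new biotechnological preparations will be added after approval and start of use in Russia".

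Sections 4.4 to 4.6 describe the analysis without mentioning calendar year or year of entry. Sex and age are the only demographic stratifiers named, and they are attached to morbidity and prevalence. Section 5.3 promises annual analyses and six-monthly interim reports but does not say what they contain.

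**The concern.** With staggered entry and a common closing date, the follow-up columns do not describe the same patients. Enrolment includes all five entry years. Each later column loses the most recent entrants, until year 4 holds the earliest cohort alone. If biologic use depends on the calendar year, as it may when products become available during the study, the columns also differ in their mix of calendar years.

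A reader will compare enrolment with years 1 to 4 and take the difference as the change patients underwent. That difference combines change within cohorts with a change in which cohorts are counted. In addition, the enrolment percentage cannot be placed in any one year. The study is descriptive, with no hypotheses (section 4.4), and no planned model would separate these components afterwards.

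**Working it through.** **Reproducing the plan's figures.** Section 3.2 sums to 2000 + 2000 + 1000 + 1000 + 1000 = 7000, the target in section 3.1. Entry from 03.2018 to 11.2022 covers 10 + 12 + 12 + 12 + 11 = 57 calendar months.

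**Assumptions.** The CRFs in section 3.2 are new patients; section 1.2 equates patients with CRFs at 7,000. There is no dropout. Each percentage is taken among patients who can reach that time point before observation closes. Use depends on calendar year only, with assumed values.

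**Who can appear in each column.** Entry is spread evenly within each period and stopped at 11.2022:

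| Column | N | Calendar years of the visits |
|---|---|---|
| Enrolment | 7000 | 2018 28.6%, 2019 28.6%, 2020, 2021 and 2022 14.3% each |
| Year 1 | 2000 + 2000 + 1000 + 917 = 5917 | 2019 to 2022 |
| Year 2 | 2000 + 2000 + 917 = 4917 | 2020 to 2022 |
| Year 3 | 2000 + 1833 = 3833 | 2021 52.2%, 2022 47.8% |
| Year 4 | 2000 × 9/10 = 1800 | 2022 only, from entrants of 03-11.2018 |

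**Pooled table with use of 5/10/15/20/25% in 2018-2022**, using whole entry years and weights 2:2:1:1:1:

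- Enrolment: (2×5 + 2×10 + 15 + 20 + 25)/7 = 90/7 = 12.9%
- Year 1: (2×10 + 2×15 + 20 + 25)/6 = 95/6 = 15.8%
- Year 2: (2×15 + 2×20 + 25)/5 = 95/5 = 19.0%
- Year 3: (2×20 + 2×25)/4 = 22.5%
- Year 4: 25.0%

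The steps between columns are 3.0, 3.2, 3.5 and 2.5 points, 12.1 in all (25.0 − 12.9). Every entry cohort in this example rises 5 points a year, and the 2018 cohort rises 25 − 5 = 20 points. Month-by-month entry gives 12.9, 15.7, 18.9, 22.4 and 25.0%, so the whole-year simplification hardly matters.

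**Range over other assumed uptake.**

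| Use 2018-2022 (%) | Pooled enrolment | Pooled year 4 | Pooled rise | Rise in 2018 cohort |
|---|---|---|---|---|
| 10 throughout | 10.0 | 10.0 | 0 | 0 |
| 5/6/8/10/12 | 52/7 = 7.4 | 12.0 | 4.6 | 7 |
| 5/7/9/11/13 | 8.1 | 13.0 | 4.9 | 8 |
| 5/10/15/20/25 | 12.9 | 25.0 | 12.1 | 20 |
| 5/15/25/35/45 | 20.7 | 45.0 | 24.3 | 40 |

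In the four rising scenarios the pooled table shows about 60 to 66% of the change that the 2018 cohort underwent.

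**The case against.** The strongest reply is that pooled tables by follow-up year are ordinary in a descriptive registry with staggered entry. Section 2.2 allows subgroups, and the dates needed for any further tabulation are collected, so it could be added at any time. This stands in part: the stated endpoints are legitimate and need not be replaced. But the permission names no subgroup, and nothing commits the analysts to an entry-year or calendar-year split.

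A reader might go further and infer that a rise across the columns would be purely calendar time, or that newly available drugs would be mistaken for treatment being stepped up. The documents do not support that. Within a patient, calendar time and follow-up time advance together, and a patient who starts a biologic once it is available has had treatment added. In the rising examples the pooled table understates a real within-cohort increase; it does not invent one.

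Three further limits are fair:

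- The evidence of changing availability is in item 104 and concerns biologics. Nothing indicates a change for maintenance OCS, ICS/LABA or LAMA.
- The therapy-change endpoint is set only to years 1, 3 and 4 and is itself a measure of change, so the point about pooled enrolment does not carry over to it.
- It might be supposed that the six-monthly reports repeat these tables, but section 5.3 does not specify their content.

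Section 4.4 does plan comparison with literature and official statistics, but for epidemiological characteristics; it does not mention treatment use.

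**Conclusion.** The point holds for biologic use. From the stated dates and recruitment table, the enrolment percentage averages five calendar years and year 4 rests on about 1,800 of 7,000 patients (25.7% before dropout), all from the 2018 cohort. The change across the columns therefore mixes cohorts and may equal no cohort's change.

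The structure follows from the plan; the size does not. It rests on assumed uptake, on reading the CRFs as new patients, on no dropout, and on use depending on calendar year alone. Under the assumed rising patterns the pooled rise was 4.6 to 24.3 points against 7 to 40 in the 2018 cohort. If use is flat there is no distortion. The documents report no uptake, so none of these is a forecast. This is a cheap improvement to the presentation of a secondary endpoint; it does not invalidate the endpoint.

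**What to change.** Keep the follow-up-year endpoints of section 2.2 as stated. In section 4.5 or 4.6, add:

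1. The biologic-use tables at enrolment and years 1 to 4 will also be shown by year of entry, so that change is read within a cohort.
2. A supplementary table will give biologic use by calendar year of visit (appendix item 3) among patients under follow-up in that year.
3. The date on which each biologic option was added to the form will be recorded and shown with these tables.

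The same split may be applied to maintenance OCS and ICS/LABA+LAMA, although the case for it is weaker.

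The cost is a few sentences of analysis text, some extra tables and a short log of form changes. No new patient data are needed, because visit dates and biologic start and end dates (items 103 and 105) are already collected. The downsides are smaller numbers per cell and a calendar-year table that mixes new entrants with retained patients; a footnote should say so.
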